The primary efficacy endpoint for the trial is 12-month local control. The papers shown below were used as reference for clinicians who determined a clinically relevant efficacy endpoint performance goal was 84% success at 12-months. This observed cryoablation group's local control rate will be tested against this performance goal.

Paper	Lesions	12-month Local Control Success	Lower 97.5% 1-sided Wilson CI
Okuneiff (2006)	125	91%	0.8469
Rusthoven (2009)	63	100%	0.9425
Baschnagel (2013)	47	97%	0.8757
Ricardi (2012)	77	94%	0.8632
Norihisa (2008)	43	94.50%	0.8337
Yoon (2006)	101	90%	0.8261

This test is accomplished by testing against the following hypotheses:

$$H_0: C_{\text{DEVICE}} \leq 84.0\%$$

$$H_a: C_{\text{DEVICE}} > 84.0\%$$

where C_{DEVICE} is the observed cryoablation local control rate at 12-months.

The null hypothesis will be rejected and the primary efficacy endpoint performance goal will be met if the lower bound of the one-sided 97.5% confidence interval for the 12-month tumor local control rate is greater than 84.0%.

PASS 12 was used to calculate the sample size needed. A sample size of 203 lesions achieves 85% power (and guarantees at least 80% power) to detect a difference ($P_1 - P_0$) of 0.0700 using a one-sided binomial test. The target significance level is 0.0250. The actual significance level achieved by this test is 0.0239. These results assume that the population proportion under the null hypothesis is 0.8400.

Power Analysis of One Proportion

Numeric Results for testing $H_0: P = P_0$ versus $H_1: P > P_0$

Test Statistic: Exact Test

Power	N	Proportion		Target Alpha	Actual Alpha	Beta	Reject H_0 If $R \geq$ This
		Given H_0 (P_0)	Given H_1 (P_1)				
0.8501	203	0.8400	0.9100	0.0250	0.0239	0.1499	181

To account for up-to a 10% 12-month lesion attrition rate, the final sample size has been increased to 226 lesions.

Note that, for the purposes for sample size calculations, the observations are assumed to be independent. However, the primary analyses will account for within subject correlation, as described below.

General Analysis Methods

Data will be analyzed using descriptive statistics. Continuous variables (e.g., age) will be summarized by the number of patients, mean, standard deviation, median, interquartile range, minimum and maximum. Categorical variables (e.g., race) will be summarized by frequencies and percentages of patients in each category. 95% confidence intervals will be calculated as appropriate.

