Analysis Populations

All primary analyses will be performed on all tumors with a Galil Medical Cryoablation System and needles as the intent-to-treat evaluable population. A supplemental per-protocol analysis

will be done for the primary endpoint, removing tumors that 1) did not have a complete treatment; and subjects who 2) did not meet the study criteria but were enrolled; or 3) had a deviation with high likelihood of affecting the study outcome (as determined by a review of all occurring deviations).

The intent-to-treat and per-protocol analyses will be compared for level of agreement. It is expected that the two populations will be similar; however, any substantial differences between the two will be analyzed appropriately to elucidate the cause of these differences. Missing data will be imputed for the primary analysis as outlined in section "Handling of Missing Data" section later in the SAP. Additional sensitivity analyses using alternate missing data imputation will be presented.

Efficacy Endpoint Analysis

Efficacy Endpoint

The primary efficacy endpoint for this study is assessment of cryoablation on local tumor control in patients with pulmonary metastatic disease at 12 months post cryoablation.

Analysis Methods

The primary efficacy endpoint for this study is defined as follows: local tumor control in patients with pulmonary metastatic disease at 12 months post cryoablation. Tumor control will be defined by the criteria defined in Section 9.7 of this protocol.

Patients are allowed up to 6 tumors and the primary efficacy endpoint (tumor control) will be calculated on a per tumor level.

The rate of local tumor control at 12-months will be analyzed using a random effects logistic regression model accounting for within subject correlation to account for multiple tumors per subject. The null hypothesis will be tested comparing the lower bound of the Wald 97.5% one-sided confidence interval for the estimated rate of local tumor control to the performance goal of 84.0%. If the lower bound is greater than 84.0%, the null hypothesis will be rejected and the endpoint will be considered met.

Safety Endpoint Analysis

Safety Endpoint

The safety endpoint for this study is to assess the incidence and severity of cryoablation related adverse events.

Analysis Methods

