The safety endpoint for this study is to assess the incidence and severity of intra-operative events, post-operative adverse events, serious adverse events and unanticipated adverse device effects related to the cryoablation procedure.

No formal hypothesis test is being made on the safety endpoints. Point estimates and two-sided 95% confidence intervals will be generated for cryoablation related adverse events.

Supportive Endpoint Analyses

Tumor control (patient level & weighted average response)

The primary efficacy endpoint is on a lesion basis. Analysis on a patient level will also be conducted in two ways. 1) Patient level: A patient must exhibit tumor control on all lesions to be considered a success using logistic regression analysis to calculate success rate and Wald 95% CI. 2) Weighted average response: patient level response rate weighted by the number of lesions that are evaluated. This will be reported as a proportion (number of successful lesions over the total number of lesions) and a 95% exact CI.

Tumor control (pulmonary metastatic disease)

Efficacy of cryoablation on local tumor control in patients with pulmonary metastatic disease at 18 and 24 months post cryoablation using a random effects logistic regression model to account for the correlation among multiple tumors per subject.

Tumor control (additional cryoablation)

Patients may receive additional cryoablation treatment(s) to the index tumor(s) initially subjected to cryoablation while participating in the study protocol. This additional cryoablation may be performed on the index tumor(s) provided that the additional treatment is performed with Galil Medical technology. In this situation, for each index lesion retreated, follow-up visits will restart per the study protocol and continue through the 24 month visit after the date of the repeat cryoablation treatment. When possible, if multiple tumors are present, all efforts should be made to align all follow up visits. For any index lesion not subjected to retreatment, the data collection continues per protocol. If additional local treatment (e.g. radiofrequency ablation, microwave ablation, surgery, radiation) is required, then the patient must be withdrawn from the study.

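### The SAP's weighted average response is the pooled lesion proportion under a patient-level label, and its exact interval is too narrow if lesions within a patient are positively correlated

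*SAP*

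**What the plan says.** The SAP, Supportive Endpoint Analyses, Tumor control (patient level & weighted average response), opens: "Analysis on a patient level will also be conducted in two ways". The first way counts a patient as a success only if every lesion is controlled, and uses logistic regression. The second is the "patient level response rate weighted by the number of lesions that are evaluated", and the SAP adds: "This will be reported as a proportion (number of successful lesions over the total number of lesions) and a 95% exact CI". No allowance for clustering is attached to that interval.

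Elsewhere the SAP treats lesions in one patient as correlated:

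- Efficacy Endpoint Analysis: "Patients are allowed up to 6 tumors and the primary efficacy endpoint (tumor control) will be calculated on a per tumor level". The 12-month rate is analysed with a "random effects logistic regression model accounting for within subject correlation to account for multiple tumors per subject".
- The 18- and 24-month control rates and tumor-level technical success, both supportive, also use random effects logistic regression.
- Sample Size Justification: "Note that, for the purposes for sample size calculations, the observations are assumed to be independent". The next sentence says that "the primary analyses will account for within subject correlation".

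**The concern.** There are two separate faults.

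1. **The label.** A reader told that there are two patient-level analyses will expect both to use the patient as the unit. The second does not. It is a lesion-level estimate, so it cannot show whether the lesion-level result depends on a few patients with many lesions.
2. **The interval.** An exact binomial interval on lesion counts assumes independent lesions. Lesions in one patient share the primary cancer, systemic treatment, operator and follow-up imaging, so positive correlation is plausible, and the SAP models it for the other tumor-level rates for which it names a model. With positive correlation the exact interval overstates precision.

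The result will sit beside the primary estimate and can be read against 84%. The lower limit of a two-sided 95% exact interval is the same number as the one-sided 97.5% exact bound in protocol section 10.1. An interval that is too narrow could therefore seem to confirm the primary result more firmly than the data do.

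**Working it through.** **Inputs from the documents.** 226 target lesions and an estimated 150 patients (mean 226/150 = 1.51); at most 6 tumors per patient; more than 10 patients with multiple lesions (SAP revision history); 203 evaluable lesions, null rate 0.84, alternative 0.91.

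**Inputs assumed.** The ICC (0 to 0.5) and the number of lesions m in each patient.

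**1. The plan's own figures.** For N = 203 with rejection at 181 or more successes, the exact binomial calculation gives alpha 0.02388 and power 0.85008, matching the stated 0.0239 and 0.8501. Attrition: 203/0.9 = 225.6, rounded up to 226. These figures assume independence, as the SAP says. The SAP gives no numerical width for the supportive interval.

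**2. The estimator.** Let patient i have x_i controlled lesions out of m_i evaluated. The lesion-weighted mean of patient rates is

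Σ[m_i · (x_i/m_i)] / Σm_i = Σx_i / Σm_i,

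which is the pooled lesion proportion. Illustration: with 1 of 1 controlled in one patient and 2 of 4 in another, the weighted mean is (1×1 + 4×0.5)/5 = 3/5, the same as 3 lesions out of 5. The unweighted patient mean is (1 + 0.5)/2 = 0.75. This step needs no assumption.

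**3. Design effect.** DEFF = 1 + ICC × (Σm²/Σm − 1), and the width grows by about √DEFF. Three assumed layouts, each with 150 patients:

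| Layout (patients × lesions) | Σm | Σm² | Σm²/Σm | DEFF at ICC 0.1 / 0.3 / 0.5 | √DEFF |
|---|---|---|---|---|---|
| A: 74×1, 76×2 | 226 | 378 | 1.67 | 1.07 / 1.20 / 1.34 | 1.03 / 1.10 / 1.16 |
| B: 106×1, 26×2, 10×3, 6×4, 2×6 | 224 | 468 | 2.09 | 1.11 / 1.33 / 1.54 | 1.05 / 1.15 / 1.24 |
| C: 110×1, 22×2, 8×3, 5×4, 3×5, 2×6 | 225 | 497 | 2.21 | 1.12 / 1.36 / 1.60 | 1.06 / 1.17 / 1.27 |

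The interval should thus be about 3% to 27% wider.

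**4. What that means for an interval.** At 91% of 203 lesions the exact 95% interval is 0.862 to 0.946. Recomputed with effective N = 203/DEFF:

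- DEFF 1.07 (N about 190): 0.860 to 0.947
- DEFF 1.60 (N about 127): 0.846 to 0.954

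**5. Coverage of the exact interval.** Beta-binomial simulation, 20,000 runs per setting, true rate 0.84 / 0.91:

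| ICC | Layout A | Layout B |
|---|---|---|
| 0 | 95.7% / 96.5% | 96.5% / 96.6% |
| 0.1 | 94.6% / 95.8% | 95.5% / 95.5% |
| 0.3 | 93.6% / 94.4% | 93.2% / 93.4% |
| 0.5 | 91.3% / 93.1% | 91.1% / 90.7% |

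Layouts near the top of the cluster range, such as C, come out lower. Over layouts with Σm²/Σm of 1.7 to 2.2, coverage is about 94–96% at ICC 0.1, 92–95% at 0.3 and 88–94% at 0.5. Treat these ranges as good to about one percentage point, because exact-interval coverage moves with the lesion total as well as the layout.

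**6. An extreme layout.** With 134 patients at 1 lesion, 1 at 2 and 15 at 6, Σm²/Σm is 3.00. At ICC 0.5 DEFF is 2.00, and coverage at a true rate of 0.84 falls to 84.1%. The stated totals allow this layout, but nothing in the documents suggests it.

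**The case against.** The strongest case on the other side has four parts.

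- **The effect may be negligible.** The exact interval is conservative: with independent lesions it covers more than 95%. At ICC 0.1 that margin absorbs most or all of the loss, and at ICC 0 the interval is not too narrow. This stands, and it limits any claim about size. A reader who applies the normal approximation, 2Φ(1.96/√DEFF) − 1, would get about 94% even at DEFF 1.07, but that formula describes a Wald interval and not the one specified.
- **No stated commitment is broken.** A reader might infer that the SAP violates its own requirement to allow for correlation. The sentence in Sample Size Justification covers only the primary analyses, so that inference fails. What remains is inconsistent practice: two other supportive tumor-level analyses do get random effects models, so supportive status alone does not explain the omission.
- **The primary conclusion is safe.** At the planned boundary, 181/203, the exact lower limit is 0.8405, and at a design effect of 1.08 it drops to 0.838. A reader might infer that the success decision is at risk. It is not: under the SAP the decision rests on the random effects model with a Wald bound, and this interval carries no test.
- **A patient-level check exists, and the formula is disclosed.** It would be wrong to infer that the plan lacks any patient-level check, because the all-lesions-controlled analysis in the same paragraph is one. The SAP also states the numerator and denominator openly, so a careful reader can see what is estimated. The list that contains it still calls it patient level.

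**Conclusion.** The point holds as a minor one. The weighted average response is the pooled lesion proportion whatever the data look like, so confidence in the labelling fault is high. Its exact interval assumes independent lesions and is too narrow if within-patient correlation is positive. Confidence in the size is only moderate, because the ICC and the lesion layout are assumed: a widening of about 3% to 27%, with little or no loss of coverage at ICC 0.1 and a loss that matters only towards ICC 0.5. The documents do not support reading this as a flaw in the primary test, as a breach of the SAP's stated commitment, or as the absence of a patient-level analysis.

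**What to change.** In the SAP, take this item out of the patient-level pair and call it the pooled lesion proportion. Replace the exact interval with one clustered on the patient: a bootstrap that resamples patients, or a Wilson or exact interval computed at the number of lesions divided by the estimated design effect. Name the chosen method in advance. Keep the all-lesions-controlled analysis as the patient-level check.

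An unweighted mean of each patient's proportion controlled could be added, but it is optional and targets a different quantity: the average patient and not the average lesion.

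The cost is a change of SAP wording, a few lines of code and a somewhat wider interval. No new data are needed.

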3.2. Previous Clinical Studies Leading Up to and Supporting the Proposed Research

Inoue et al has reported on the safety and feasibility of percutaneous cryoablation for lung tumors. This study included 396 lung tumors in 117 (104 with metastatic disease) consecutive patients conducted in 193 cryoablation sessions. All patients tolerated the procedure well. The mean follow up period was 899± 778 days. Adverse events were categorized using the CTCAE system. Pneumothorax was the most common complication observed in 61.7% of the treatment sessions. Of these, 10.9% of the cases required chest tube insertion, comparable to that associated with RF ablation. Delayed and recurrent pneumothorax each occurred in 30 of the treatment sessions, resulting in 17 chest tube insertions. Risk factors predictive of pneumothorax were male sex, and greater number of cryoneedles. The authors theorize the higher pneumothorax rate may be related to the number of cryoneedles used, thicker modified coaxial system, and the modality used to detect pneumothorax. Pleural effusion occurred in 136 treatment sessions and required no additional treatment. No CTCAE grade 4 or 5 events were observed. Three grade 3 complications were noted; one in which an empyema required fenestration and 2 cases of pneumothorax which required pleurodesis. Inoue et al concluded that percutaneous cryoablation is minimally invasive and associated with improved safety.³²

Yamouchi et al reported the use of percutaneous cryoablation for pulmonary metastases from colorectal cancer on 24 patients for 55 tumors during 30 treatment sessions. Follow up scans were performed every 3-4 months after treatment. Pneumothorax was reported in 19 sessions with only 1 session requiring insertion of a chest tube. A small amount of pleural effusion occurred in 21 sessions, none of which required a chest tube. The 1- and 3-year local progression free intervals were 90.8% and 59%, respectively. The 1- and 3-year overall survival rates were 91% and 59.6%, respectively.³³

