5.3. Other Data to be Assessed

Other data for this study include, but are not limited to:

- Overall patient survival post cryoablation;
- Time to metastatic lung disease progression beyond the index tumor(s);
- Time to overall cancer progression;
- Time to untreatable metastatic lung disease control with cryoablation;
- Time to untreatable metastatic lung disease control with focal therapy;
- Efficacy of cryoablation on local tumor control for each index tumor in patients with pulmonary metastatic disease at 18 and 24 months post cryoablation;
- Efficacy of cryoablation on local tumor control for each index tumor in patients with pulmonary metastatic disease undergoing additional cryoablation treatment(s) of a previously treated index tumor;
- Cryoablation technical success (See Section 10.5.5);
- Changes in physical function and quality of life over time (See Section 10.5.5).

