10.5.3. Primary Endpoint

The primary endpoint for this study is defined as follows: efficacy of cryoablation on local tumor control for each index tumor in patients with pulmonary metastatic disease at 12 months post cryoablation.

Patients are allowed up to 6 tumors and the primary efficacy endpoint (tumor control) will be calculated on a per tumor level. To be considered a success each tumor treated during the baseline procedure must meet the tumor control criteria at the 12 month follow-up visit.

The local tumor control counts and rates will be presented along with the 95% two-sided confidence intervals for the rates. The rate numerator will be defined as the number of tumors experiencing tumor control at 12-months. The rate denominator will be defined as the total number of tumors evaluated at 12-months.

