Demographics, disease status, imaging data, lung function, and protocol deviations will be summarized using descriptive statistics. These measures include but may not be limited to:

Demographics

- Age at the date of consent
- Sex
- Race and ethnicity (Per French regulations, race and ethnicity will not be collected at any study site in France.)
- Height, weight, and BMI
- Comorbidities
- Smoking history
- Concomitant medications

Disease status

- Primary cancer diagnosis
- Prior treatment(s) for lung metastases
- Lung or other metastatic disease
- Baseline laboratory data

Index Tumor(s)

- Histology of primary tumor
- Proof of metastases
- Location of the index tumor(s) in the lung(s)
- Size of the index tumor(s)
- Number of index tumors
- Number of new tumors

Procedure/Discharge

- Number of tumors treated with cryoablation
- Index tumor size measurement:
 - 3 axes of measurements (cm) and
- Number and type of cryoablation needles used
- Freeze and thaw times, per cycle
- Number and type of intra-operative complication(s)
- Severity of complication(s)
- Requirement for hospital admittance/stay
- Requirement for surgical intervention(s)

All protocol deviations

Study Completion/Withdrawals

Subject Disposition

Subject disposition will be presented as:

- Number of subjects enrolled

- Number of subjects completing each follow-up visit
- Number of subjects withdrawn or lost to follow-up
- Number of subject deaths
- Number of subjects evaluable for ITT and PP analyses

Randomization and Blinding

As this is a single arm study, no randomization or blinding will be performed. To minimize selection bias within the enrolled patient population, participation in the study is to be offered to all eligible patients on a consecutive basis as they present to the physician at the site.

Handling of Missing Data

Missing data will be prospectively minimized through training of the participating investigator and site staff, and through appropriate clinical trial management. Every effort will be made to collect all data points in the study. All patient data that is available on patients who drop out during the course of the study will be included where possible. Sensitivity analyses will be conducted to determine the effect of missing data on the primary efficacy endpoint.

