For the formal primary endpoint hypothesis test, patients with missing 12-month tumor evaluations will be imputed using multiple imputation (SAS PROC MI using FCS logistic regression and including tumor status at prior visits), except in the following case where previous visit evidence can be used to impute 12-month status:

- Subjects with local tumor failure at 6-months will be considered a local tumor failure at 12-months post-index procedure.

Additional sensitivity analyses to be conducted:

- Worst case: all missing data are imputed to be failures
- Best case: all missing data are imputed to be successes
- Complete case: all missing data are treated as missing and not imputed

Subset Analyses

Analysis will be done on outcomes for subgroups including, but not limited to, gender and lesion size. Additional non-protocol defined subgroups include: number of needles used, number of lesions, primary cancer diagnosis, and lesion location.

Poolability Analyses

A poolability analysis among investigational centers and geographies (US/OUS) will be performed for the primary efficacy endpoint. This analysis will be performed on the ITT population.

Poolability of Sites

Combining of Small Sites

Sites contributing less than 5 subjects to the as treated analysis set will be considered “small sites” and ordered by the date of first enrollment in the as treated analysis set. Starting with the first “small site”, a pseudo-site will be created by adding subjects from successive “small sites”. If the number of subjects reaches or exceeds the size of the median enrollment of the “large sites”, then a second pseudo-site will be created. Additional pseudo-sites, if needed, would be created in the same manner.

Primary Endpoint by Site

Among sites and pseudo-sites, the proportions of subjects who achieve local tumor control at 12 months will be compared using logistic regression. If the resulting p-value is ≤ 0.05 , further exploratory analysis will attempt to identify covariates (baseline characteristics) that may explain differences among the sites. Otherwise, the data will be considered to be poolable across study sites.

Poolability of Geographies

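### The SAP does not carry earlier local failures into the 18- and 24-month control rates, so failed tumors can drop out of those rates or re-enter as controlled

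*SAP*

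**What the plan says.** Protocol section 5.3 lists the late outcome among the other data to be assessed: "Efficacy of cryoablation on local tumor control for each index tumor in patients with pulmonary metastatic disease at 18 and 24 months post cryoablation". The SAP (Supportive Endpoint Analyses, Tumor control (pulmonary metastatic disease)) gives it one sentence, with the analysis "at 18 and 24 months post cryoablation using a random effects logistic regression model". The random effect is there for several tumors in one patient. No denominator is stated, and there is no rule for missing scans, earlier failure, retreatment or death.

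The rules that do exist are tied to month 12 (SAP, Handling of Missing Data):

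- Imputation: "For the formal primary endpoint hypothesis test, patients with missing 12-month tumor evaluations will be imputed using multiple imputation".
- Carry-forward: "Subjects with local tumor failure at 6-months will be considered a local tumor failure at 12-months post-index procedure".
- Sensitivity: "Sensitivity analyses will be conducted to determine the effect of missing data on the primary efficacy endpoint".

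Two treatment provisions in Protocol section 7.8, repeated in the SAP under Tumor control (additional cryoablation), affect tumors that have failed. Other local therapy to an index tumor means the patient is withdrawn. Repeat cryoablation restarts that lesion's visits and runs them to a new month 24. Protocol section 8.7 defines local tumor control as no local failure having occurred.

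**The concern.** If control means that no local failure has occurred, a tumor that has failed cannot become controlled later, and the rate in a fixed set of tumors cannot rise. The sponsor's own 6-to-12-month rule treats failure as permanent, but it stops at month 12.

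After that, the two treatment provisions act mainly on tumors that have failed, because local failure is an obvious reason for retreatment or other local therapy. A logistic model fitted visit by visit omits tumors with no outcome unless told otherwise. The late rates could then look better than the experience of the treated tumors, and the denominator would be settled after the data are seen. These are the per-tumor durability figures that readers are likely to quote.

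**Working it through.** **Plan's own figures.** The documents give no rate, sample size or attrition for 18 or 24 months, so there is nothing to reproduce there. The 12-month design does reproduce: exact binomial, 203 tumors, reject at 181 or more, alpha 0.0239, power 0.8501; 203/0.90 = 225.6, rounded up to 226. Its 10% attrition allowance covers month 12 only.

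**Step 1: follow a tumor whose failure is first recorded at month 12.**

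- No further local treatment: CT stays scheduled at 18 and 24 months (Protocol 7.7). Judged against the nadir (8.7.4), it remains failed while it stays at least 20% above that nadir. Section 8.7 also mentions comparison with the preceding interval's scan; on that reading, a tumor that fails and then stays the same size could be scored as controlled.
- Other local therapy: the patient is withdrawn, so there is no 18- or 24-month scan.
- Re-cryoablation: the visits restart. The SAP has a separate summary at 12 months after retreatment, but does not say how the lesion counts in the main late rates.

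**Step 2: size of selective exit.** Let S be true control at the visit and f the share of failed tumors that leave. Assume controlled tumors stay, or are lost for reasons unrelated to their status. Then

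reported control = S / [S + (1 − S)(1 − f)].

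The documents give no value for f, so a range is shown. Three values of S are used:

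- 0.84, assumed (it equals the 12-month performance goal);
- 0.91² = 0.828, the planned 12-month rate with constant hazard;
- √(0.908 × 0.59) = 0.732, log-linear interpolation of the 1- and 3-year local progression-free figures in the 24-patient colorectal series cited in Protocol 3.2.

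| S | f = 25% | f = 50% | f = 75% |
|---|---|---|---|
| 84.0% | 87.5% | 91.3% | 95.5% |
| 82.8% | 86.5% | 90.6% | 95.1% |
| 73.2% | 78.5% | 84.5% | 91.6% |

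For the first row: 0.84/(0.84 + 0.16 × 0.75) = 0.84/0.96 = 0.875; 0.84/0.92 = 0.913; 0.84/0.88 = 0.955. In the second row, f = 75% takes reported control from 91% at month 12 to 95.1% at month 24, while the true rate falls to 82.8%.

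If failed tumors re-enter as controlled instead of leaving, reported control is S + (1 − S)f. At S = 0.84 and f = 25%, that is 0.84 + 0.04 = 88.0%.

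**Step 3: death.** The same series reports "The 1- and 3-year overall survival rates were 91% and 59.6%, respectively". Interpolated 24-month survival is √(0.91 × 0.596) = 0.736, about 0.74. Take S = 0.84 and f = 50%.

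- No deaths: 0.84/(0.84 + 0.08) = 91.3%.
- Equal death loss: (0.84 × 0.74)/(0.84 × 0.74 + 0.08 × 0.74) = 0.6216/0.6808 = 91.3%, unchanged.
- Deaths only among controlled tumors: 0.6216/(0.6216 + 0.08) = 88.6%, which is lower.

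For death alone, let RR be the failure risk in tumors of patients who died relative to survivors. The failure rate among survivors is (1 − S)/(0.736 + 0.264 × RR). With S = 0.732:

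- RR = 1: control 73.2%, no bias;
- RR = 2: 0.268/1.264 = 0.212, control 78.8% (+5.6 points);
- RR = 0.5: 0.268/0.868 = 0.309, control 69.1% (−4.1 points).

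At this survival, about 226 × 0.264 ≈ 60 tumors would have no 24-month scan because of death.

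**The case against.** The strongest reply is that the SAP is silent, and silence is not a method. A reader might infer that the late model uses only tumors still being scanned, but no text says so. The protocol's denominator, "The rate denominator will be defined as the total number of tumors evaluated at 12-months", concerns month 12. The SAP also says "All patient data that is available on patients who drop out during the course of the study will be included where possible", without limiting this to month 12. Since control means no local failure, an analyst could already count a recorded failure as lasting. Failure alone does not end imaging. This stands in part: the observed-only analysis is the default of the named model, not a stated rule. But the sentence on dropouts says nothing about how an earlier failure is scored, and needing an explicit rule for month 12 suggests the definition was not thought sufficient alone.

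A reader might also infer that deaths inflate late control. Step 3 does not support that: equal death loss changes nothing, and unequal loss can move the rate either way. Death needs a stated rule because of the number of tumors involved.

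Nor are these the only durability results. The SAP plans a Kaplan-Meier summary of time to lung disease progression under local disease progression. It is not stated to be per tumor, and its reference date is the patient's first procedure, so it supplements the per-tumor late rate without replacing it.

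Finally, the endpoint is supportive and has no hypothesis test. That stands and limits the weight of the point.

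**Conclusion.** The concern holds as a gap with a likely direction. The plan gives failed tumors two routes out of, or back into, the late series and has no rule at 18 or 24 months that keeps them as failures. Selective exit or re-entry biases late control upward.

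With assumed true 24-month control of 84%, the overstatement is 3.5, 7.3 or 11.5 points for exit of 25%, 50% or 75% of failed tumors. With the interpolated 73.2%, it is about 5 to 18 points. These are illustrations: the exit share is unknown, and both true rates are assumptions. No particular number of points should be presented as the expected bias, and none of it should be attributed to death without knowing how death relates to local failure. The 12-month primary conclusion is unaffected.

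**What to change.** Amend the SAP for the 18- and 24-month analyses:

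1. Score any index tumor with an earlier local failure as a failure, including one later re-cryoablated or withdrawn for other local therapy after failure. State also how a tumor counts if it is retreated with no recorded failure.
2. Apply the primary's multiple imputation, and the worst-, best- and complete-case analyses, to tumors of living patients with missing scans.
3. Report, by visit, the number of tumors evaluable and the number missing because of death.
4. Add, as a supportive analysis and not a replacement, tumor-level cumulative incidence of first local failure, timed from that tumor's ablation, with death as a competing event and patient-clustered confidence intervals.

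Item 4 answers a different question from the logistic rate. With independent constant hazards, 16% failure and 26% death at 24 months, the hazards are −ln 0.84 = 0.174 and −ln 0.74 = 0.301. Cumulative incidence is (0.174/0.475) × (1 − 0.84 × 0.74) = 13.9%, so its complement is 86.1%, not 84%.

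Item 1 has its own asymmetry if tumors that failed before death are kept while tumors controlled at death are excluded: 0.6216/(0.6216 + 0.16) = 79.5% against 84%. The SAP should say which tumors of deceased patients enter the denominator, and items 3 and 4 should be read beside the rate.

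The cost is SAP text and a little more analysis from data already collected. The reported late control rates will probably be less favorable.
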